4.1.4 Survival

Survival will be determined over two years from entry into the study by either periodic medical record review for patients seen in the SIU Neuro-Oncology Clinic, or by search of the Social Security Death Index (SSDI). Volumetric analysis will be performed with Tera-recon software on gadolinium contrast-enhanced T1W MRI to assess extent of resection (EOR) and residual tumor volume (RTV). These findings will then be correlated with progression free survival (PFS) and overall-survival (OS).

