10.1.1 Extent of Resection

Volumetric MRI techniques measure difference in the areas of bright MRI signal when a post-operative T1 non-enhanced image is compared to a post-operative T1 gadolinium enhanced image. These differences may be measured by postprocessing digital subtraction techniques (dsMRI – see section 2.4) or by outlining areas of new bright signal as judged by the neuroradiologist. Extent of resection is divided into three categories which are defined as follows:

- Gross-total tumor resection (GTR) of tumor is defined as no measureable residual contrast enhancement in the immediate post-operative MRI.

- Near-total resection (NTR) is defined as measureable post-operative residual contrast enhancement greater than or equal to the volume of one MRI voxel (0.175 cm³) and less than or equal to 2.5 cm³.
- Incomplete resection (IR) is defined as measureable post-operative residual contrast enhancement greater than 2.5 cm³.
- 10.2 Guidelines for Evaluation of Measurable Disease

All neuroradiological measurements should be taken and recorded in metric notation using standardized volumetric techniques. These techniques have been discussed previously.^{7,11,12}

- 10.3 Confirmatory Measurement/Duration of Response
 - 10.3.1 Confirmation N/A
 - 10.3.2 Duration of Overall Response N/A
 - 10.3.3 Duration of Stable Disease N/A

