Fluorescence vs. Tumor Density	Tumor	No Tumor
Fluorescence	a (Number of areas identified)	b (Number of areas identified)
No Fluorescence	c (Number of areas identified)	d (Number of areas identified)

Sensitivity=a/(a+c); specificity=d/(b+d)

Third, the following grid will be used to examine the sensitivity/specificity of white light examination of the tumor bed and tumor density:

White Light		
Examination vs. Tumor	Tumor	No Tumor
Density		
White Light Obvious	a (Number of areas	b (Number of areas
Tumor	identified)	identified)
White Light Obvious No	c (Number of areas	d (Number of areas
Tumor	identified)	identified)

Sensitivity=a/(a+c); specificity=d/(b+d)

Fourth, the following grid will be used to examine the relationship of the neurosurgeon's intraoperative fluoroscopic aided estimate of the extent of

IRB NUMBER: 12-135

resection vs. the actual extent of resection as measured by post-operative MR imaging techniques (See definitions in section 10.1.1), specifically a Cohen's kappa will be calculated to assess the strength of agreement between operative EOR and MRI EOR:

Operative EOR vs. MRI EOR	MRI GTR	MRI NTR	MRI IR
	(Number of	(Number of	(Number of
Operative GTR	areas	areas	areas
	identified)	identified)	identified)
	(Number of	(Number of	(Number of
Operative NTR	areas	areas	areas
	identified)	identified)	identified)
	(Number of	(Number of	(Number of
Operative IR	areas	areas	areas
	identified)	identified)	identified)

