12.2 Sample Size/Accrual Rate

It is anticipated that this trial will accrue a mimimum of 3 patients and a maximum of *18 patients in the phase 1 portion of this protocol and 16 patients in the phase 2 portion of the trial. (*Due to four patients receiving 40mg/kg rather than three, 19 total patients will be studied in phase 1. Protocol deviation approved by IRB on 17 Oct 2013.)

Total accrual of a maximum of 34 patients in 48 months is expected.

Assuming that the estimated success rate of resection is 0.70, with a sample size of 34, we will have 80% power to detect a moderate kappa of 0.490 from the null hypothesis of zero intraclass kappa, using a large sample 0.050 level two-sided test.

Descriptive statistics will be presented as mean and standard deviation for continuous variables, as frequency and percentage for categorical variables. SAS 9.1 will be used to perform the statistical analyses, type I error (significance level) will be set as 0.05.

32

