Time:	□ Blue	☐ Strongly Fluorescent☐ Weakly Fluorescent☐ No Fluorescence	
	□ White	☐ Obvious Tumor☐ Obvious Not Tumor	
Time:	□ Blue	☐ Strongly Fluorescent ☐ Weakly Fluorescent ☐ No Fluorescence	
	□ White	☐ Obvious Tumor☐ Obvious Not Tumor	
Time:	□ Blue	☐ Strongly Fluorescent ☐ Weakly Fluorescent ☐ No Fluorescence	
	□ White	☐ Obvious Tumor ☐ Obvious Not Tumor	
Time:	□ Blue	☐ Strongly Fluorescent ☐ Weakly Fluorescent ☐ No Fluorescence	

Grade	Definition		
0	No fluorescence. No difference between any of the tissues	No	
	visualized.	fluorescence	
+	Low fluorescence. Red glow is barely distinguished from surrounding non-fluorescent tissue.	Weak	
++	Moderate fluorescence. Dull red glow of fluorescent tissue.	fluorescence	
+++	High fluorescence. Bright red glow of fluorescent tissue	Strong fluorescence	

Estimate	of extent of fluorescent tiss	sue
resected	(%):	

Estimate of extent of enhancing tumor resected (%):

C-6

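### Primary objective 1.1.3 reduces two continuous measures of extent of resection to three classes and a kappa with no weights stated, which hides the direction and size of the surgeon's error and costs some power

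*Combined protocol and SAP*

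**What the plan says.** Objective 1.1.3 is one of three primary objectives. It sets the surgeon's intra-operative judgement of extent of resection against what imaging shows afterwards.

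- **Surgeon's side.** The Intra-Operative Data Sheet in Appendix C asks for a percentage: "Estimate of extent of enhancing tumor resected". Section 4.1.2 instead describes the judgement as an estimate of remaining volume.
- **MRI side.** Section 4.1.4 plans volumetric software measurement of EOR and residual tumor volume, to be correlated with progression-free and overall survival. The calendar in Section 9 includes a pre-study gadolinium MRI.
- **Classes.** In Section 10.1.1, "Extent of resection is divided into three categories which are defined as follows": gross-total (GTR, nothing measurable left), near-total (NTR, 0.175 to 2.5 cm³) and incomplete (IR, above 2.5 cm³).
- **Analysis.** The fourth grid of Section 12.1.2 crosses operative with MRI class, and "a Cohen's kappa will be calculated to assess the strength of agreement between operative EOR and MRI EOR". No weighting, difference, intraclass correlation or limits of agreement is specified.
- **Power.** Section 12.2 reads "Assuming that the estimated success rate of resection is 0.70, with a sample size of 34", and claims "80% power to detect a moderate kappa of 0.490 from the null hypothesis of zero intraclass kappa".
- **Form.** The Post-operative Data page of Appendix C holds only the MRI class. It has no volume or percentage field.

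**The concern.** A comparison of an estimate with a measured value should say whether the surgeon over- or under-estimates, and by how much. A kappa gives neither. The off-diagonal cells of the grid show direction only when a class boundary is crossed, and never size. To illustrate with the Section 10.1.1 cut-points: readings of 2.4 and 2.6 cm³ would count as a disagreement, while 3 and 30 cm³ would count as full agreement.

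Three further problems follow from the same choice.

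- With no weights, a GTR/IR disagreement counts the same as a GTR/NTR one, although the classes are ordered.
- The surgeon's sheet is in percent and the classes are in residual cm³. Without a conversion rule, the operative margin of the grid is not reproducible.
- Cutting and unordered scoring can cost power. The trial is capped at 34 patients, and this kappa is the only kind of statistic for which the plan states a power.

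**Working it through.** **1. The plan's own figure.** Inputs from Section 12.2: N = 34, kappa 0.490 against 0, rate 0.70, two-sided 0.05. For a binary intraclass kappa the null variance is 1/N, so

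power = Φ(0.49 × √34 − 1.96) = Φ(2.857 − 1.960) = Φ(0.897) = 81.5%.

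The N for 80% power is ((1.960 + 0.842)/0.49)² = 32.7, so 33. The stated 80% reproduces. It belongs to a two-category kappa with a single rate, not to the planned three-class table.

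**2. Precision.** The variance of a binary kappa k at prevalence p is

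(1−k)[(1−k)(1−2k) + k(2−k)/(2p(1−p))]/N.

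With k = 0.49 and p = 0.70 this is 0.51 × [0.0102 + 1.7617]/34 = 0.9037/34. The standard error is 0.163 and the 95% half-width is 1.96 × 0.163 = 0.32. An observed 0.49 would carry an interval of about 0.17 to 0.81.

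**3. Cost of the classes.** The documents give no NTR/IR split, no latent correlation and no distribution of the continuous values. I therefore assumed:

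- a bivariate-normal latent residual for surgeon and MRI;
- that success at 0.70 means GTR, so 70% of values on each side are tied at complete resection;
- that the binary kappa at that cut is 0.49, which gives a latent correlation of 0.712.

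Simulated power at N = 34, two-sided 0.05 (40,000 runs; type I error 4.7% to 5.2% for every test):

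| NTR/IR share (%) | Unweighted kappa | Linearly weighted kappa | Spearman, tied at GTR | Spearman minus unweighted |
|---|---|---|---|---|
| 25/5 | 77.2 | 86.3 | 88.8 | 11.6 |
| 20/10 | 78.2 | 88.5 | 89.0 | 10.8 |
| 15/15 | 80.9 | 88.6 | 88.7 | 7.8 |
| 10/20 | 83.7 | 87.6 | 89.1 | 5.4 |
| 5/25 | 84.0 | 85.0 | 88.7 | 4.7 |

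Allowing for differences between simulation runs, the loss is about 4 to 11 points, with the most lopsided split (25/5) nearer 12.

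**4. Where the loss comes from.** At 15/15, weighting alone recovers 88.6 − 80.9 = 7.7 of the 7.8 points. Across the table, the gap left between weighted kappa and the rank test is 0.1 to 3.7 points.

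**5. Sensitivity.**

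- If 0.49 is read as the three-class kappa, the latent correlation is 0.79 to 0.83 for splits 25/5 to 10/20. Unweighted kappa then has 89% to 95% power, and the loss is about 2.5 to 6 points. Both anchors together give about 2.5 to 12.
- With no ties at complete resection, Pearson reaches 99.9% at correlation 0.712. The gap to unweighted kappa is then 99.9 − 84.0 = 15.9 to 99.9 − 77.2 = 22.7 points.
- Away from the Section 12.2 anchor the size moves again. At latent correlation 0.60 and split 20/10, the powers are 58.8% and 72.9%, a gap of 14.1 points.

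**The case against.** Several points on the other side have force.

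- **The classes have a clinical basis.** Section 2.2.2 makes gross-total resection the aim of surgery and defines it by absent enhancement. Whether the surgeon judges GTR correctly is a proper categorical question. This stands, and is why the grid should stay.
- **Most of the power loss is not due to cutting.** A reader might infer that reweighting the classes recovers nothing. The table shows otherwise for power. What weighting cannot recover is the size of error within a class.
- **The large gains are not realistic.** A reader might infer a loss of about 20 points, or power above 99% on the continuous scale. That needs no pile-up at complete resection. Section 10.1.1 defines GTR as nothing measurable left, so if the 0.70 means GTR, about 70% of values are tied.
- **A rank test is not an agreement analysis.** A surgeon who always overestimates by a fixed amount still correlates perfectly. The power comparison in the working is about association, so correlation can only support the main analysis.
- **The data are not quite ready to use.** The post-operative form lacks a continuous field. Section 4.1.4 (volumetry on enhanced T1 images) and Section 10.1.1 (enhanced against non-enhanced difference, by subtraction or outlining) also describe the MRI measurement differently. The cm³ pairs used as illustration are hypothetical, since the surgeon's sheet records percent.

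None of this supplies a reason to leave the continuous comparison out.

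**Conclusion.** The point holds on its main ground. A primary objective about how an estimate compares with a measurement is analysed in a way that cannot report the size of the error and shows its direction only through class changes. It ignores class order and lacks a rule for assigning the surgeon's class. This conclusion rests on the text alone and needs no power model.

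The power cost is secondary and conditional: about 4 to 11 points under the Section 12.2 anchor with values tied at complete resection, and about 2.5 to 12 over the other anchor and splits examined. It assumes a latent-normal model and that success means GTR, neither of which the documents state. Figures up to about 23 points should not be headlined.

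A reader might also infer that the stated 80% is a conservative floor for a continuous analysis. The documents do not support that: the figure is for a binary kappa, and no power was derived for an agreement measure on percent EOR. The change is worth making, but the existing grid is not invalid.

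**What to change.** **Section 12.1.2, objective 1.1.3.** Add a patient-level continuous agreement analysis of the surgeon's percentage of enhancing tumor removed against MRI volumetric percent EOR. The latter looks derivable as 100 × (1 − residual volume / pre-operative volume), given the pre-study MRI. Report:

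- the mean difference with limits of agreement, read with care because values pile up at 100%;
- an intraclass or concordance correlation with a bootstrap 95% CI;
- a rank correlation only as a supporting test of association.

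Keep the GTR/NTR/IR grid, scored with a linearly weighted kappa and its 95% CI. State how the surgeon's percentage, or the remaining volume in Section 4.1.2, is converted to a class.

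**Appendix C, Post-operative Data.** Add a field for MRI residual volume or percent EOR.

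**Sections 4.1.4 and 10.1.1.** State which MRI measurement is the reference for objective 1.1.3.

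**Section 12.2.** Say only that the 80% refers to a binary intraclass kappa, and do not describe it as a floor for other analyses.

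**Cost.** One data field, some wording and a little analysis code. No additional patients or scans are needed. The drawback is the ceiling at 100%, which calls for cautious reading of the limits of agreement.

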12. STATISTICAL CONSIDERATIONS

- 12.1 Study Design/Primary Endpoints
 - 12.1.1 Establish a safe dose for oral 5-ALA administration NCI Common Toxicity Criteria will be used to quantify toxicity following 5-ALA administration. Special attention will be paid to rash, pruritis, hepatic transaminitis, nausea and vomiting. Based on previously reported German trial, a 30 mg/kg dose is anticipated to be as well-tolerated as 10 and 20 mg/kg doses.
 - 12.1.2 Determine the sensitivity and specificity of the Phase 1 recommended dose in discriminating between normal and malignant tissue intraoperatively.

Four methods are being employed to assess discrimination of tumor from normal brain tissue.

- The neurosurgeon will assess the ability to distinguish tumor from normal brain tissue under ultraviolet illumination and grade the discrimination from 0 to +++ (3+) (See Section 8.1.1). Although arguably the most relevant measure, this is also the most biased and difficult to corroborate measure.
- Under white light the neurosurgeon will assess and biopsy an area of obvious tumor and an area of obviously normal (but possibly edematous) non-eloquent brain. The neurosurgeon will then assess whether these

IRB NUMBER: 12-135

- areas correspond to areas of strong, weak or no fluorescence seen under blue light.
- Under blue light, the neurosurgeon will assess the areas of fluorescence in the tumor cavity and will biopsy areas of strong fluorescence, weak fluorescence and no fluorescence. It may not be necessary to repeat some of these biopsies if the area has already been biopsied under white light. The pathologist will score tumor involvement in each biopsy specimen.

These data will be placed in the following grids – first a 3x3 grid as follows for an analysis of correlation, specifically a Cohen's kappa will be calculated to assess the strength of agreement between fluorescence and tumor density:

Fluorescence vs. Tumor Density	Solid Tumor	Infiltrating tumor/normal brain	No tumor (edematous peritumoral normal brain)
High Fluorescence	(Number of areas identified)	(Number of areas identified)	(Number of areas identified)
Weak Fluorescence	(Number of areas identified)	(Number of areas identified)	(Number of areas identified)
No Fluorescence	(Number of areas identified)	(Number of areas identified)	(Number of areas identified)

Second, these data will also be placed in a simpler 2x2 grid for fluorescence sensitivity/specificity analysis:

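### Section 12.1.2 names no weights for Cohen's kappa on two ordered 3x3 grids, so by default a two-category error counts the same as a one-category error

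*Combined protocol and SAP*

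**What the plan says.** Section 12.1.2 sets up two 3x3 grids. For the first, a Cohen's "kappa will be calculated to assess the strength of agreement between fluorescence and tumor density". For the fourth grid, which compares the surgeon's intraoperative estimate with postoperative MRI, a Cohen's "kappa will be calculated to assess the strength of agreement between operative EOR and MRI EOR". Neither sentence mentions weights, and the word unweighted does not appear either.

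Section 10.1.1 states: "Extent of resection is divided into three categories which are defined as follows". The categories are cuts of residual enhancing volume: none measurable (GTR), 0.175 to 2.5 cm³ (NTR) and more than 2.5 cm³ (IR). The other grid crosses none, weak and strong fluorescence with no tumor, infiltrating tumor and solid tumor.

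Section 12.2 holds the only power statement: "we will have 80% power to detect a moderate kappa of 0.490". Its inputs are 34 patients, a resection success rate of 0.70, an intraclass kappa of zero under the null, and a large-sample test, two-sided at 0.05. It does not name the grid it serves, but a success rate of resection points to EOR. The EOR comparison is primary objective 1.1.3.

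**The concern.** All the categories are ordered, and kappa without weights ignores order. A surgeon who judges the resection gross-total when more than 2.5 cm³ remains is scored exactly as one who misses a small residual. Objective 1.1.3 asks how closely the surgeon's estimate follows the imaging, so the size of an error carries information that the planned statistic discards. Section 12.1.2 also introduces the fluorescence grid as a correlation analysis, which sits poorly with a statistic that is blind to order.

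If the weights stay unstated, they could also be chosen after the tables are seen, when different versions of kappa can differ noticeably on the same data.

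**Working it through.** **1. The plan's own power figure.** Inputs from section 12.2: success rate p = 0.70, N = 34, kappa 0.490 against zero, two-sided 0.05. A single success rate implies a binary rating. With q = 1 − p, the goodness-of-fit test for a binary intraclass kappa has cells p² + κpq, 2pq(1 − κ) and q² + κpq. Against κ = 0 the noncentrality is

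N·κ²·p²q²·(1/p² + 2/(pq) + 1/q²) = N·κ²·(q² + 2pq + p²) = N·κ² = 34 × 0.49² = 8.163.

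Power = Φ(√8.163 − 1.96) = Φ(0.897) = 81.5%, and the N needed for 80% is 7.849/0.2401 = 32.7, so 33. The stated 80% therefore reproduces. The formula uses no 3x3 structure, so weights cannot change it.

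**2. What unweighted kappa hides.** The documents give no cell counts, so these two tables are illustrative. They assume one EOR entry per patient and 35 patients (19 in phase 1 per the footnote, plus 16 in phase 2). Rows are operative GTR/NTR/IR and columns are MRI GTR/NTR/IR.

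- Table A: [20, 4, 0], [2, 3, 1], [0, 1, 4]. There are 27 agreements, and all 8 errors are adjacent.
- Table B: [20, 0, 4], [1, 3, 1], [2, 0, 4]. There are 27 agreements, with 2 adjacent and 6 extreme errors.

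κ = (po − pe)/(1 − pe), where po = Σ w·n/35 and pe = Σ w·(row total × column total)/35².

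Unweighted:
- A: po = 27/35 = 0.7714; pe = (24·22 + 6·8 + 5·5)/1225 = 601/1225 = 0.4906; κ = 0.551.
- B: po = 0.7714; pe = (24·23 + 5·3 + 6·9)/1225 = 621/1225 = 0.5069; κ = 0.536.

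Linear weights (1, 0.5, 0):
- A: po = (27 + 0.5·8)/35 = 0.8857; adjacent products 24·8 + 6·22 + 6·5 + 5·8 = 394; pe = (601 + 197)/1225 = 0.6514; κ = 0.672.
- B: po = (27 + 0.5·2)/35 = 0.8000; adjacent products 24·3 + 5·23 + 5·9 + 6·3 = 250; pe = (621 + 125)/1225 = 0.6090; κ = 0.489.

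Quadratic weights (1, 0.75, 0):
- A: po = 33/35 = 0.9429; pe = 896.5/1225 = 0.7318; κ = 0.79.
- B: po = 28.5/35 = 0.8143; pe = 808.5/1225 = 0.6600; κ = 0.45.

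| Weights | Table A | Table B |
|---|---|---|
| None | 0.55 | 0.54 |
| Linear | 0.67 | 0.49 |
| Quadratic | 0.79 | 0.45 |

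**3. Does weighting change power?** This was simulated with N = 34, 100,000 multinomial tables per scenario, the null standard error and a two-sided 0.05 test. The margins are assumptions: GTR 0.70 with NTR/IR 0.20/0.10, 0.15/0.15 and 0.10/0.20. Ordered disagreement comes from a latent bivariate normal.

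| Scenario | Unweighted | Linear |
|---|---|---|
| Ordered disagreement, unweighted κ = 0.49 | 93–95% | 97–98% |
| Disagreement unrelated to order, κ = 0.49 | 92–93% | 87–89% |
| Ordered, weaker (latent correlation 0.5, unweighted κ about 0.23–0.26) | 43–48% | 53–54% |

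Two flatter sets of margins (thirds; 0.40/0.30/0.30) gave the same directions: 98% against over 99%, 98% against 94–95%, and 51% against 66–67%.

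**The case against.** **Silence is not a choice.** The plan says only Cohen's kappa, so unweighted is an inference. That is correct, but it is the ordinary default, and if weights were intended the plan still leaves them open. The same sentence cures both.

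**Exact agreement is a legitimate target.** Section 2.2.2 defines the surgical goal as no enhancing tumor on the immediate postoperative scan, and section 12.2 works with a success rate. On that view any residual is a failure. The filled-in 3x3 table would also show gross errors whatever kappa is used. This stands: it would be too strong to say that unweighted kappa fails to measure anything clinically relevant, and it is a reason to keep it as a companion statistic.

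**A reader might infer that unweighted kappa costs the trial power on its only powered comparison.** The documents do not support that. The 80% is for a binary intraclass kappa and is unaffected by weights. Large gains from weighting appear only at agreement well below the planned 0.490. Near 0.490 linear weighting gains a few points if disagreement follows the order and loses a few if it does not. Ordered errors are plausible, because the MRI categories cut one volume and the surgeon records a percentage resected, but the documents give no cell probabilities to settle it.

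**The fluorescence grid matters less.** Objective 1.1.2 is served by sensitivity and specificity from the 2x2 grid, so weighting there is a refinement.

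**Linear weights are a convention.** Nothing in the documents shows that GTR to NTR and NTR to IR are equal steps, and the illustrative tables show that the choice affects the result. That argues for fixing the weights in advance.

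**Conclusion.** The point holds as a specification gap with a cheap, better alternative. Both grids are ordered, no weights are named, and under the default a two-category error costs no more than a one-category error. In the illustrative tables the default separates two very different error patterns by about 0.01 (0.55 and 0.54), while linear weights separate them by 0.18 (0.67 and 0.49). Those sizes depend on hypothetical tables; the insensitivity to order does not.

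No claim about lost power is made. Power near the planned kappa moves only a few points, in a direction set by an unknown disagreement pattern. What the check does show is a mismatch: section 12.2 powers a binary intraclass kappa, while section 12.1.2 analyses three categories. The plan should say so.

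**What to change.** In section 12.1.2:

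- Pre-specify linear-weighted kappa (weights 1, 0.5, 0) with a 95% confidence interval for operative against MRI EOR.
- Specify the same for fluorescence against tumor density, labelled as a secondary refinement. Patients contribute several areas to that grid, so its interval should allow for clustering by patient.
- Report unweighted kappa and the full 3x3 table beside each weighted kappa.

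In section 12.2, state that the 80% power refers to a binary intraclass kappa with a success rate of 0.70, and not to the three-category statistic.

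The cost is SAP wording only: no new data or patients, and weighted kappa is standard software output. The downside is that the weights are conventional. Fixing them before analysis and reporting both statistics deals with that.
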